to the HB-adMSCs and Placebo groups, respectively. Safety assessments will be ongoing. Complete Blood Count, Comprehensive Metabolic Profile and Coagulation Panel will screen for hepatotoxicity, renal failure or alterations in the coagulation cascade that might entail a safety concern for the individual. Efficacy assessments will include PHQ-9, SF-36, TNF-a, IL-6, IL-10, and CRP.

The trial is designed to be conducted over 3 periods or phases:

- **Phase 1** (screening): Our screening process starts with a telephone call to provide a general overview of the study and discuss eligibility requirements. The study patient will receive the informed consent document by e-mail or in the pre-paid envelope provided. If, after reviewing this consent the study patient is still interested in participating in the study, he/she will need to sign and return the consent form to Hope Biosciences Stem Cell Research Foundation. This process can take up to 45 days.
- **Phase 2** (Treatments): Includes Infusion 1 (Week 0), Infusion 2 (Week 2), Infusion 3 (Week 6), Infusion 4 (Week 10) and Infusion 5 (Week 14). Subjects will be monitored at the clinical site for 1 hours following HB-adMSCs administration.
- **Phase 3** (follow-up): Includes Follow Up Week 18, 22 and End of Study at Week 26.

Selection and Withdrawal of Patients

Inclusion Criteria

Inclusion Criteria:

1. Men, and women 18 years of age or older
2. Participant works in a capacity that is characterized as high-risk or very high-risk
 - a. High-Risk Exposure jobs are those with high potential for exposure to known or suspected sources of COVID-19.
 - First responders, health care delivery and support staff (e.g., law enforcement, fire fighters, paramedics, doctors, nurses, and other hospital staff who must enter patients' rooms) exposed to individuals potentially having COVID-19.
 - Mortuary workers involved in preparing (e.g., for burial or cremation) the bodies of people who are known to have, or suspected of having, COVID-19 at the time of their death
 - b. Very High-Risk Exposure jobs are those with high potential for exposure to known or suspected sources of COVID-19 during specific medical, postmortem or laboratory procedures.
 - Health care workers (e.g., doctors, nurses, dentists, paramedics, emergency medical technicians) performing aerosol-generating procedures (e.g., intubation, cough induction

Allogeneic HB-adMSCs to provide immune support against COVID-19.

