- procedures, bronchoscopies, some dental procedures and exams or invasive specimen collection) on known or suspected COVID-19 patients
- Health care or laboratory personnel collecting or handling specimens from known or suspected COVID-19 patients (e.g., manipulating cultures from known or suspected COVID-19 patients)
 - Morgue workers performing autopsies, which generally involve aerosol-generating procedures, on the bodies of people who are known to have, or suspected of having, COVID-19 at the time of their death
3. No signs or symptoms of infection, including but not limited to, body temperature >100 F and pulse rate > 100 BPM.
 4. Subject provides written informed consent prior to initiation of any study procedures.
 5. Agrees to the collection of venous blood per protocol.
 6. Agrees to conformational testing for SARS-CoV-2 before end of study.

Exclusion Criteria

1. Women who are pregnant or lactating, or those who are not pregnant but do not take effective contraceptive measures
2. Patients who are participating in other clinical trials or have intake of investigational drug within the previous 30 days;
3. Inability to provide informed consent or to comply with test requirements;
4. Any medical disease or condition that, in the opinion of the site PI or sub-investigator, precludes study participation. Including acute, subacute, intermittent or chronic medical disease or condition that would place the subject at an unacceptable risk of injury, render the subject unable to meet the requirements of the protocol, or may interfere with the evaluation of responses or the subject's successful completion of this trial.
5. Patients who have received a stem cell treatment within one year.
6. Receipt of any other SARS-CoV-2 or other experimental coronavirus vaccine at any time prior to or during the study.
7. Patient currently or recently symptomatic for COVID-19 or anyone with COVID-19 associated symptoms within the past 30-days

Withdrawal, Removal, and Replacement of Patients

Patients will be considered to have completed the study if they complete treatment and assessments through Week 26. A patient's investigational treatment should be discontinued if any of the following situations occurs:

- The Investigator believes that for safety reasons, it is in the best interest of the patient to stop treatment.
- The patient is non-compliant with the study visit schedule or other protocol requirements.

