Unblinding of patient and researcher will occur in the case of adverse event suspected to be related to the investigational product, per the medical monitor and DSMB.

Regulatory authorities and/or the IRB may request the unblinding of data from one or more patients at any time.

Prior and concomitant conditions

The investigators should document all prior significant medical history. Additional conditions present at the time when informed consent is given and up to the time of first infusion (Week 0) are to be regarded as concomitant conditions. Illnesses first occurring or detected during the study and/or worsening of a concomitant condition during the study should be documented as AEs in the CRF.

Prior and concomitant medications

All medications, including over-the-counter treatments and preventative vaccines taken by the patient during the study, including those treatments initiated prior to the start of the study, must be recorded in the CRF. The entry must include the dose, regimen, route, indication, and dates of use.

Study Procedures

Table 2 outlines the timing of procedures, and assessments to be performed throughout the study.

Table 2. Schedule of Assessments

Visit Number	1	2	3	4	5	6	7	8	9
Weeks	N/A	Week 0	Week 2	Week 6	Week 10	Week 14	Week 18	Week 22	Week 26
Visit Name	Screening (Phone call)	Infusion-1 /Baseline	Infusion 2	Infusion 3	Infusion 4	Infusion 5	Follow Up	Follow Up	EOS
Window Period	Up to 45 days	±4 days	±4 days	±4 days	±4 days	±4 days	±4 days	±3 days	±3 days
STUDY PROCEDURES									
Informed Consent	X	X							
Inclusion and Exclusion Criteria	X	X							
Pre-infusion assessment		X	X	X	X	X			
Review of Medical History	X	X	X	X	X	X	X	X	X
Concomitant Medication Review	X	X	X	X	X	X	X	X	X

Allogeneic HB-adMSCs to provide immune support against COVID-19.

Vital Signs		X	X	X	X	X	X	X	X
Weight and Height ¹		X	X	X	X	X	X	X	X
Physical Examination		X	X	X	X	X	X	X	X
SF-36 Questionnaire		X	X	X	X	X	X	X	X
PHQ-9		X	X	X	X	X	X	X	X
Rapid antibody COVID-19		X							X
CBC with differential		X		X		X			X
Chemistry		X		X		X			X
Coagulation Panel		X		X		X			X
CRP		X		X		X			X
IL-6		X		X		X			X
IL-10		X		X		X			X
TNF alpha		X		X		X			X
HB-adMSCs Administration		X	X	X	X	X			
24-hour telephone encounter		X	X	X	X	X			
Adverse Event Monitoring		X	X	X	X	X	X	X	X
1. Height will only be measured at baseline									

Informed Consent (ICF)

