A complete physical examination (head, eyes, ears, nose, throat, heart, lungs, abdomen, skin, cervical and axillary lymph nodes, neurological, and musculoskeletal systems) will be performed

Allogeneic HB-adMSCs to provide immune support against COVID-19.

at baseline visit. In addition, medical history (including smoking history) will be recorded at baseline.

A limited physical examination to verify continued patient eligibility and to follow up any change in medical history will be performed at the visits indicated in the schedule of assessments. Symptom-driven physical examinations will be performed as clinically indicated at any study visit. All changes not present at baseline or described in the past medical history and identified as clinically noteworthy will be recorded as AEs.

Clinical Laboratory Parameters

The Investigator must review all laboratory reports and document the review. Any laboratory test result or change considered by the Investigator to be clinically significant should be considered an AE and recorded in the AE CRF. Clinically significant abnormal values occurring during the study will be followed until repeat test results return to normal, stabilize, or are no longer clinically significant.

Laboratory tests to be performed during the study:

Complete Blood Count with Differential	IL-6
Chemistry	IL-10
Coagulation study (PTT/PT/INR)	Tumor Necrosis Factor alpha
C Reactive Protein	Rapid Antibody Test for COVID-19

Adverse Events

An AE is any symptom, physical sign or disease that either emerges during the study or, if present at screening, worsens during the study, regardless of the suspected cause of the event. All medical and psychiatric conditions (except those related to the indication under study) present at screening will be documented in the medical history CRF. Changes in these conditions and new symptoms, physical signs, or diseases should be noted on the AE CRF during the rest of the study.

Clinically significant laboratory abnormalities should also be recorded as AEs. Surgical procedures that were planned before the patient enrolled in the study are not considered AEs if the conditions were known before study inclusion; the medical condition should be reported in the patient's medical history.

Serious Adverse Events (SAE)

A serious adverse event (SAE) is any AE that is:

Allogeneic HB-adMSCs to provide immune support against COVID-19.

- fatal
- life-threatening
- requires or prolongs hospital stay

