5.3 Examination of Covariates, Other Strata and Subgroups

5.3.1 Covariates and Other Strata

Baseline will be included as a covariate in the efficacy analyses, wherever applicable.

Protocol Number: HBCOVID02
Hope Biosciences
Statistical Analysis Plan

Confidential

Date: 14-Oct-2021
Version: 1.0
Status: Final

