5.3.2 Examination of subgroups

No subgroup analysis planned.

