7. EFFICACY ANALYSES

7.1. Primary Efficacy Analyses

7.1.1. Endpoint / Variables

The primary endpoints are incidence of COVID-19 symptoms and Hospitalizations due to COVID-19 symptoms after Week 26 end of study.

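### Week 0 COVID-19 antibody status is collected but never used, so prior infection can shrink the primary risk difference and fall unevenly between small arms by chance

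*Protocol*

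**What the plan says.** - **Collection.** Protocol Table 2 marks "Rapid antibody COVID-19" at Week 0 and Week 26 only. The protocol's list of laboratory tests names "Rapid Antibody Test for COVID-19" without saying how the result will be used.
- **Eligibility.** Inclusion 2 selects for exposure: "Participant works in a capacity that is characterized as high-risk or very high-risk". Exclusion 6 keeps out vaccine-acquired immunity: "Receipt of any other SARS-CoV-2 or other experimental coronavirus vaccine at any time prior to or during the study". For infection, the nearest rule is exclusion 7: "Patient currently or recently symptomatic for COVID-19 or anyone with COVID-19 associated symptoms within the past 30-days". Screening is a telephone call, so no antibody result exists before Week 0.
- **Endpoints.** SAP 7.1.1: "The primary endpoints are incidence of COVID-19 symptoms and Hospitalizations due to COVID-19 symptoms after Week 26 end of study". Both are yes/no outcomes. The objectives describe the symptoms as fever, cough or breathing difficulty, and no text makes a positive test part of the symptom endpoint.
- **Analysis.** SAP 7.1.2 takes the difference in proportions as the summary measure, and SAP 5.1, 5.4 and 7.1.4.1 give unadjusted two-sample comparisons. SAP 5.3.1 says "Baseline will be included as a covariate in the efficacy analyses, wherever applicable", but the models that carry a baseline term are those for the continuous secondary endpoints. SAP 5.3.2 says "No subgroup analysis planned".
- **Randomization.** Neither document describes stratification.

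**The concern.** In a prevention trial, immunity at entry is a strong candidate predictor of the outcome. The plan treats the two sources of immunity differently: vaccination is excluded, while infection more than 30 days earlier, or without symptoms, is not. The trial already measures antibody status before the first infusion and then leaves it aside.

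Two things are at stake. Protected subjects add to both denominators but little to the event counts, which shrinks a difference in proportions. And with about 13 placebo subjects, an uneven split of previously infected subjects is quite possible; a reader of the results could not tell how far it explained the observed difference. If serostatus is examined only after unblinding, whatever it shows is post hoc.

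**Working it through.** **No plan figure to reproduce.** The protocol sets the sample size by the number of patients banked or registered to bank. It gives no attack rate, effect size, power or seroprevalence, so the sizes below illustrate stated assumptions.

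**Inputs from the documents.** N = 53 at 3:1: 53 × 3/4 = 39.75, about 40 on HB-adMSCs, and 53/4 = 13.25, about 13 on placebo and in each dose arm. SAP 5.4 names the overall comparison (40 vs 13); SAP 7.1.4.1 specifies each dose against placebo (13 vs 13). Tests are two-sided at 5%.

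**Assumptions.** Antibody-positive share s = 10%, 20% or 30%. Risk in antibody-negative subjects 20% on placebo and 10% on active, with 30% vs 15% and 40% vs 20% as alternatives. Antibody-positive subjects have no events (worst case).

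**Step 1, dilution.** Risk difference = (p0 − p1)(1 − s).
- 20% vs 10%: 0.10 × 0.9, 0.8, 0.7 = 0.09, 0.08, 0.07.
- 30% vs 15%: 0.15 × 0.9, 0.8, 0.7 = 0.135, 0.120, 0.105.

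**Step 2, chance of a gap of 20 points or more in seropositivity.** Exact enumeration of two independent binomials with common proportion s:

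| s | 40 vs 13 | 13 vs 13 |
|---|---|---|
| 10% | 4.2% | 9.6% |
| 20% | 11.7% | 21.5% |
| 30% | 16.4% | 28.3% |

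**Step 3, effect of such a gap with no drug effect.** Shift = gap × risk in antibody-negative subjects = 0.20 × 0.20 = 0.04, or 0.06 and 0.08 at risks of 30% and 40%. At a 20% event rate the standard error is √[0.16 × (1/40 + 1/13)] = 0.128 for 40 vs 13 and √[0.16 × 2/13] = 0.157 for 13 vs 13. A 4-point shift is therefore 0.04/0.128 = 0.31 or 0.04/0.157 = 0.25 of a standard error.

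**Step 4, type I error.** Pooled z test by exact enumeration, s = 20%, risks of 20-40% in antibody-negative subjects:
- Averaged over all allocations, null rejection is 3.6-5.9%.
- Given a 13 vs 13 split of 1 and 5 antibody-positive subjects, it is 4.6%, 7.0% and 9.8% at risks of 20%, 30% and 40%. With 3 in each arm it is 3.0%, 3.7% and 4.0%.
- For the 1 and 5 split at 40% risk, a Mantel-Haenszel stratified test brings 9.8% down to about 6%.

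**Step 5, power for 40 vs 13.** The last column takes only the antibody-negative subjects: 36 vs 12, 32 vs 10 and 28 vs 9.

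| Risks | s = 0 | s = 10%, 20%, 30%, all subjects | s = 10%, 20%, 30%, antibody-negative only |
|---|---|---|---|
| 20% vs 10% | 17.3% | 15.7%, 14.2%, 12.8% | 16.5%, 16.9%, 16.1% |
| 30% vs 15% | 24.9% | 22.7%, 20.4%, 18.1% | 24.0%, 21.7%, 19.9% |

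**The case against.** The best defence is that randomization already deals with this. Antibody status at Week 0 precedes treatment, so any imbalance is due to chance, and the test's error rate allows for chance. A reader might infer from the unused test that the comparison is systematically confounded. The documents do not support that: unconditional type I error stays near 5% (step 4), and a typical shift is a fraction of a standard error (step 3). One qualification remains. SAP 4 limits the efficacy set to subjects who received all five infusions, so balance in the analysed set is not fully protected by randomization. Serostatus stratification does not repair that.

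Other points stand in part:
- **Full protection is an upper bound.** The symptom endpoint does not require a positive test, so an antibody-positive worker with a cough from another cause can still count as an event.
- **Seroprevalence is unknown.** Occupational exposure and a protocol version dated January 2021 make prior infection plausible, but neither document gives a rate or enrolment dates.
- **The test is not the only information on prior infection.** Medical history is recorded and is among the planned study-population summaries in SAP 6.1, so known past COVID-19 could be compared by arm. The test adds unrecognised infection.
- **A display may exist.** SAP Appendix 5 is not in the text reviewed, so a serostatus listing cannot be ruled out. A listing would not be a pre-specified analysis.
- **Enrolling all exposed workers is defensible** given the protocol's high-risk-population objective.

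**Conclusion.** The gap is real and worth closing. The plan collects a relevant baseline variable and assigns it no role. Under the assumed 10-30% seropositivity, the risk difference loses up to 10-30% of its size. A gap of 20 points or more between groups has probability 4-16% for the pooled comparison and 10-28% for a single dose against placebo. That gap would move the null difference by about 4 points at 20% risk and up to 8 points at 40%.

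Three stronger conclusions are tempting but not supported: systematic bias or an inflated overall error rate; antibody-positive subjects contributing no events, which is only the worst case; and a need to make the antibody-negative subjects the primary population. That last step would change the target population, leave about 9-12 placebo subjects and gain 1-3 percentage points of power at the rates in step 5. It would not restore randomization while the five-infusion condition remains.

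Low power, 17-25% for a halving of risk in step 5 even with nobody immune, is the larger limitation and is unaffected by this point.

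**What to change.** Make these changes before unblinding:
1. **SAP 5.3.1 and 7.1.4.1:** pre-specify a primary-endpoint comparison stratified by Week 0 antibody status, for example an exact or Mantel-Haenszel stratified test with a stratified risk difference. State how sparse strata and missing results will be handled.
2. **SAP 6.1:** tabulate Week 0 antibody status by arm.
3. **SAP 5.3.2:** replace the statement that there are no subgroup analyses with one supportive analysis in Week 0 antibody-negative subjects. Keep antibody-positive and antibody-negative subjects together as the main population.
4. **Supportive outcome:** report Week 0-negative to Week 26-positive conversion by arm, overall and with vaccinated subjects identified. Vaccination during the study is a post-randomization event, so a result restricted to unvaccinated subjects must be read with that caution. Conversion would help separate prevented infection from suppressed symptoms.

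Items 1 and 3 do different work. Stratifying addresses imbalance, but a risk difference averaged over both strata is still diluted; the antibody-negative analysis shows the effect in subjects without detected prior infection.

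The cost is SAP wording, since both tests are already scheduled. Downsides are sparse strata, a small antibody-negative placebo group, misclassification by a rapid test, and little recovered power. The return is mainly better balance and a result that can be interpreted.

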- results in persistent or significant disability or incapacity
- Important Medical Events (IME): those events that may not result in death, be immediately life threatening, or require hospitalization. They may be considered a SAE when, based upon medical judgement, they may jeopardize the subject and may require intervention to prevent one of the other serious outcomes noted above. For example, drug overdose or abuse, a seizure that did not result in in-patient hospitalization, or intensive treatment of bronchospasm in an emergency department would typically be considered serious. (FDA, 21CFR312.32; ICH E2A and ICH E6)

All SAEs must be reported to Hope Biosciences immediately after the Investigator becomes aware of the event, along with a determination as to whether it is associated with the study drug. Patients will be instructed to report AEs at each study visit. All AEs are to be followed until resolution or until a stable clinical endpoint is reached.

Each AE is to be documented in the CRF with reference to onset date, duration, frequency, severity, relationship to study drug, treatment of event, and outcome. Furthermore, each AE is to be classified as being serious or non-serious. Changes in AEs and resolution dates are to be documented in the CRF.

For the purposes of this study, the period of observation for collection of AEs extends from the time the patient gives informed consent through Week 26 (or early discontinuation visit). Follow-up of the AE is required until the event resolves or stabilizes at a level acceptable to the Investigator.

Intensity of Adverse Event

The intensity of the AE will be judged based on the following:

- Mild: Awareness of sign(s) or symptom(s) which is/are easily tolerated
- Moderate: Enough discomfort to cause interference with usual activity
- Severe: Incapacitating or causing inability to work or to perform usual activities

Causal Relationship of Adverse Events

Medical judgement will be used to determine the relationship, considering all relevant factors, including pattern of reaction, temporal relationship, de-challenge and confounding factors such as concomitant medication, concomitant disease and relevant history. Assessment of causal relationship will be recorded in the CRF.

- **Definitely Related:** The adverse event is clearly related to the investigational product –

Allogeneic HB-adMSCs to provide immune support against COVID-19.

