i.e. an event that follows a reasonable temporal sequence from administration of the study intervention, follows a known or expected response pattern to the suspected intervention, that is confirmed by improvement on stopping and reappearance of the event on repeated exposure and that could not be reasonably explained by the known characteristics of the subject's clinical state.

- **Possibly Related:** An adverse event that follows a reasonable temporal sequence from administration of the study intervention follows a known or expected response pattern to the suspected intervention, but that could readily have been produced by a number of other factors.
- **Not Related:** The adverse event is clearly not related to the investigational product. - i.e. another cause of the event is most plausible; and/or a clinically plausible temporal sequence is inconsistent with the onset of the event and the study intervention and/or a causal relationship is considered biologically implausible.

Investigator Reporting: Notifying the Study Sponsor

Any study-related unanticipated problem posing risk to subjects or others, and any type of serious adverse event, will be reported to Hope Biosciences (Sponsor) by telephone within 24 hours of the event. To report such events, a Serious Adverse Event (SAE) form will be completed by the investigator and electronically faxed to the sponsor within 24 hours to [contact]. The investigator will keep a copy of this SAE form on file at the study site.

Within the following 48 hours, the investigator will provide further information on the Serious Adverse Event or unanticipated problem in the form of a written narrative. This should include a copy of the completed Serious Adverse Event form, and any other diagnostic information that will assist the understanding of the event. Significant new information on ongoing Serious Adverse Events should be provided promptly to Hope Biosciences.

Routine Study Close-out

The study will end when Hope Biosciences has obtained all data necessary to complete its studies of the investigational product. Standard procedures may include, but is not limited to, review of regulatory documents, collection of completed case report forms, reconciliation of study records, removal or destruction of ancillary study supplies, and informing the Investigator of remaining obligations (e.g., record retention, final report submission to the IRB, financial disclosure updates, etc.).

Infusion Stopping Rules

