It is the responsibility of the Principal Investigator to oversee the safety of the study at his/her site. This safety monitoring will include careful assessment and appropriate reporting of adverse events as noted above. At Hope Biosciences, [name], MD [contact] will be responsible for reviewing any reported AEs and SAEs to determine if changes to the study need to be made or if the study should be stopped for the protection of patients. DSMB will review all deaths (to assure non-attribution), cases of anaphylaxis or suspected anaphylaxis, thromboembolic events, new malignancy/tumor, infections/hospitalizations (including unrelated to COVID-19 but due to underlying condition). After 15 subjects diagnosed with COVID-19, 5 subjects are hospitalized, or 3 subjects in the ICU, DSMB will review. DSMB will also review safety data at mid-point of the study.

Risks

Potential Risks of the Investigational Product and Clinical Investigation

Risks Associated with HB-adMSCs

Respiratory Risks:

A potential risk is that the infusion could initiate a VTE event with subsequent cardiopulmonary sequelae of respiratory failure and/or right heart strain/failure. We plan to monitor oxygen saturation, and respiratory rate/work of breathing for the first 2 hours post- infusion. The patient will be examined for VTE events (clinical exam, oxygen saturation) during each infusion visit and at each follow-up visit.

Hepatic Risks:

The reticuloendothelial system can sequester immature blood elements, theoretically resulting in hepatic injury. An acute elevation of the AST/ALT hepatic enzymes > 900 U/dl post-infusions will be considered an infusion related adverse event. This level is based upon the organ system scoring definitions for moderate hepatic failure and corresponds to the CTCAE v4.03 Grade 4 adverse event. It is unlikely that "end vessel" micro-thrombosis would occur in the liver due to the dual blood supply of the liver and the lung is the first pass organ. A CMP will be obtained at follow-up visits.

Coagulation Cascade:

A coagulation panel will be obtained at screening, baseline, infusion and the follow-up visits. The patient will be monitored for the development of venous thromboembolic events (see pulmonary monitoring above) as well as for the development of clinical deep vein thrombosis (limb swelling, tenderness, discoloration).

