The risks associated with this cellular product are currently unknown and have not been studied in this population, to date. There is a potential risk of increased vulnerability to COVID-19, worsening of the disease, and/or complications from the disease. Although currently not

Allogeneic HB-adMSCs to provide immune support against COVID-19.

observed in HB-adMSCs, risks of infusion with MSCs include infusion-related reactions, thrombogenesis or malignancy.

The types of risk associated with HB-adMSCs are also stated in the Informed Consent Form (See ICF)

Minimization of Risks

Although the risk to subjects participating in the study is anticipated to be minimal, the clinician, at his/her discretion, will not collect data from those individuals for whom collection is judged to pose an unusually high risk of physical or mental harm or discomfort.

Participation in this study poses moderate risk to study personnel related to potential pathogens that may be present in the subject's specimens which are then expanded during the culture process. These risks will be minimized by adherence to the principles of universal precautions and by conducting the planned testing on blood from the subject at screening for particular pathogens of concern.

Personnel should wear appropriate personal protective equipment to avoid contact of the eyes or skin with hazardous materials or products derived from biological sources.

Subjects will be advised to follow current federal guidelines regarding COVID-19 such as the following:

- Use hand sanitizer that contains at least 60% alcohol
- Avoid touching your eyes, nose, and mouth with unwashed hands
- Avoid close contact
- Adhere to social distancing guidelines and maintain at least 6' of distance with others

General procedures for personnel include:

- Hands must be washed with soap and water for at least 20 seconds, if soap and running water are unavailable, an alcohol-based hand rub with at least 60% alcohol will suffice this action. Always wash hands that are visibly soiled.
- Avoid touching their eyes, nose or mouth.
- Healthcare workers will wear:
 - o Gowns
 - o Gloves
 - o Disposable surgical masks.
 - o Eye/face protection (e.g., goggles, face shield)
- Surfaces where subjects have been in contact will be disinfected 70% Isopropyl Alcohol, hydrogen peroxide, or Clorox disinfectant.

Allogeneic HB-adMSCs to provide immune support against COVID-19.

Potential Benefits

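### Read literally, the causality definitions give no level to some plausibly timed adverse events that are novel or were not rechallenged, so these drop out of the related-AE count

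*Protocol*

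**What the plan says.** The protocol section Causal Relationship of Adverse Events defines three levels.

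- **Definitely Related:** plausible timing, a known or expected response pattern, no reasonable explanation in the subject's clinical state, and an event "that is confirmed by improvement on stopping and reappearance of the event on repeated exposure".
- **Possibly Related:** an event that "follows a known or expected response pattern to the suspected intervention, but that could readily have been produced by a number of other factors", in addition to plausible timing.
- **Not Related:** clearly unrelated, because another cause is most plausible, the timing does not fit, or a causal link is biologically implausible.

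There is no probable, unlikely or unassessable level. The lead-in gives the assessor discretion: "Medical judgement will be used to determine the relationship, considering all relevant factors". It names de-challenge among the factors to weigh but does not name rechallenge.

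Relatedness is then used in the secondary endpoint on drug-related AEs and SAEs (Protocol, Study Endpoints; SAP 2.1) and in the AE overview by relation to treatment (SAP 8.1). The SAP adds no definition of its own.

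**The concern.** The two related levels do not meet in the middle. An event with a competing explanation can be Possibly Related. The same event without one, which is stronger evidence against the product, must meet the full rechallenge standard or it has no related level at all. The known-pattern condition sits in both related levels, so a new kind of reaction cannot enter either.

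This matters more here than for an established product, because the protocol says: "The risks associated with this cellular product are currently unknown and have not been studied in this population, to date". What is at stake is the completeness of a secondary safety endpoint and of one SAP summary. An event left without a level is not counted as related.

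**Working it through.** No numerical figure in the plan is at issue, so the check is one of logic. Code each event by five features taken from the definitions:

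- T: timing plausible (yes/no)
- K: known or expected pattern (yes/no)
- R: improvement on stopping and reappearance on re-exposure (yes/no)
- O: other cause (none / could readily have produced it / most plausible)
- B: biologically implausible (yes/no)

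This gives 2 × 2 × 2 × 3 × 2 = 48 profiles. The levels as written are:

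- Definitely = T and K and R and O none
- Possibly = T and K and O at least could readily
- Not Related = not T, or O most plausible, or B

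**Profiles with a ground for Not Related**

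- Timing not plausible: 2 × 2 × 3 × 2 = 24.
- Timing plausible but biologically implausible: 2 × 2 × 3 = 12.
- Timing plausible, not implausible, another cause most plausible: 2 × 2 = 4.
- Total 24 + 12 + 4 = 40, which leaves 48 − 40 = 8.

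**The remaining 8** (timing plausible, not biologically implausible, no most plausible other cause)

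| Other cause | Known, rechallenge confirmed | Known, not rechallenged | Novel, rechallenge confirmed | Novel, not rechallenged |
|---|---|---|---|---|
| None | Definitely | no level | no level | no level |
| Could readily have caused it | Possibly | Possibly | no level | no level |

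One profile is Definitely, two are Possibly and five have no level (1 + 2 + 5 = 8). These are counts of logical cases and say nothing about how often each occurs.

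**Whether the empty cells can arise in this trial**

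- *Novel:* the protocol itself says that the risks in this population are unknown (Risks Associated with HB-adMSCs).
- *Not rechallengeable, fatal:* no re-exposure is possible.
- *Not rechallengeable, dosing ended:* treatment stops if "The Investigator believes that for safety reasons, it is in the best interest of the patient to stop treatment", or after a severe allergic reaction (Withdrawal, Removal, and Replacement of Patients).
- *Not rechallengeable, late onset:* the fifth and last infusion is at Week 14 (Investigational Plan), while "the period of observation for collection of AEs extends from the time the patient gives informed consent through Week 26". An event first seen in those last 26 − 14 = 12 weeks has no later infusion on which to reappear.

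**The case against.** The strongest reply is that the governing sentence is discretionary. An assessor told to use medical judgement will put an event that is neither clearly related nor clearly unrelated at Possibly Related, and the endpoint is then unaffected. The trial has one site, which limits inconsistency between assessors. The protocol also lists anticipated risks (thromboembolism, hepatic injury, infusion reactions, malignancy), which narrows what counts as novel.

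Much of this stands. It is why the effect may be zero. It does not remove the defect. Filing the event as Possibly Related departs from that level's written conditions, and nothing names Possibly Related as the default. The list of anticipated risks does not help an expected event with no other cause that was never rechallenged.

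Four stronger readings are tempting, and the documents do not support them.

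- *That a literal assessor would file these events as Not Related.* That level needs one of three grounds. These events lack the first two and meet the third only if judged biologically implausible. The literal result is no level.
- *That the committee's vocabulary in Study Alteration Rules must map to this scale.* The committee makes its own determination, and its terms already group into three actions: continue, deliberate or stop.
- *That the hepatic rule contradicts the scale.* It reads: "An acute elevation of the AST/ALT hepatic enzymes > 900 U/dl post-infusions will be considered an infusion related adverse event". Study Alteration Rules separates the drug from the infusion as a cause, so this label need not be a level on the product scale.
- *That the loss can be stated in percentage points.* The documents give no basis for the number of affected subjects.

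**Conclusion.** The definitions leave a real gap. A plausibly timed event with no other cause that is novel, or that was not or cannot be rechallenged, meets neither related level. It meets Not Related only if a causal link is judged biologically implausible. A novel event with ready alternatives, none of them most plausible, is uncovered as well. Taken literally, these events are not counted in the related-AE endpoint or in the SAP summary by relation.

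The size is unknown and may be zero, because it depends on how assessors use their discretion. The conclusion assumes that the listed conditions are read as jointly required, which is how they are worded.

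A reader might infer that safety oversight fails. It does not. Stopping rule 1 already acts on a death possibly associated with the drug, and rules 2 to 5 do not use this scale. The DSMB reviews all deaths (Medical Monitoring). SAP 8.1 tabulates all AEs and SAEs and lists individual events whatever their relation. AE analysis is descriptive, so no test or error rate is affected. The point is worth correcting because the change is small and specific.

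**What to change.** Redefine Possibly Related as the residual level: timing is reasonable, a causal relation cannot be excluded, and the event meets neither Definitely Related nor Not Related. Drop its known-pattern and alternative-cause conditions. In the table under the check, all five empty cells then become Possibly Related, giving one Definitely and seven Possibly.

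Leave Definitely Related, Not Related and Study Alteration Rules as they are. Relaxing the rechallenge condition in Definitely Related is not advised. If the committee's wording were ever tied to the scale, that change would lower the threshold at which a definitely related SAE stops the study.

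The cost is a wording change, re-review of AEs already classified, and possibly a slightly higher related-AE count. The new level yields to Not Related. An event that can now be read into both levels, because other factors could have produced it and one is most plausible, would therefore go to Not Related. The re-review should check for such cases.
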